Answers to these important question, can be used to not only enrich our understanding of the mechanisms important to the microbiome-immune system relationship, but will directly inform future decision in colon cancer treatment. Most important, these results may uncover potential therapeutics for cancer treatment and side-affect mitigation, such as chemotherapy-induced diarrhea, which affects over 50% of patients undergoing anti-cancer therapy for CRC. For example, it may be prudent to first restructure the microbiome to establish a more conducive environment prior to treatment to enable the most effective treatment response. Further, it may be possible to leverage the immune system by engineering probiotics that deliver anti-inflammatory cytokines that ameliorate inflammation after treatment. **Conducting this study is a significant part of the key steps in elucidating causal mechanisms underlying the impact of the microbiome-immune system relationship on efficacy of anti-cancer therapy, and determining the impact of diet and metabolite fluctuations in predicting recurrence and survival.**

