- A. After pre-study consent, the day prior to colonoscopy for colon cancer screening/detection, a stool (patient-collected) sample will be collected prior to bowel prep for colonoscopy. If, for some reason, this is not possible to do by the patient, then the physician will collect a rectal swab during colonoscopy (**Visit 1**). One stool sample (self-collected) the day prior to the first outpatient appointment before start of treatment (between Days 21-28) – Pre-Treatment (**Visit 2**) 3. Once IV chemotherapy begins, this will be designated at treatment day 1 (TD1). After the IV chemo rounds 2 (**Visit 3, treatment day 15**), 6 (**Visit 4, treatment day 71**) and 10 (**Visit 5, treatment day 128**), stool will be collected by the patient at home the day before starting chemo and on the 2nd day (or within 72 hours to account for constipation/diarrhea) after the last treatment day of that round of IV chemo for that session. Specifically, one stool will be collected on TD 15 and 19 (or the day before the next IV chemo round starts) after the 2nd round of IV chemo; on TD, 71 and 75 (or the day before the next IV chemo round starts) after the 6th round of IV chemo; and on TD 128 and 131 (or the day before the next round of IV chemo) after 10th round of IV chemo treatment. Blood draw is SOC, however, stool samples will be requested in addition to SOC.
- B. A blood sample taken at the same time as blood is draw for standard clinical treatment when the patient goes in for the clinical visit or treatment by the REA during usual blood draw times (Surgery Day and on the outpatient visit prior to treatment; Treatment Days 15, 71, 128).
- C. Tissue samples from the patient's resected tumor and non-tumor adjacent tissue after resection surgery will be collected for 1) fresh/frozen and 2) Carnoy's fixitive. Specifically, the physician will take a larger piece of both tumor and non-tumor adjacent tissue so that a small piece of each can be stored for analysis. After specimen collection and ID coding, microbial DNA will be isolated from the microbiome specimens and fecal and circulating metabolites identified. The DNA will be used to conduct microbial DNA sequencing (metagenomics) in accordance with existing protocols through the Integrated Human Microbiome Project (iHMP) study of IBD. The fecal metabolites will be used

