##### **Study procedures:**

This study will collect two sets of data from subjects at baseline (pre-treatment) and on-treatment, as outlined in the Study Design section above.

After specimen collection and coding, microbial DNA will be isolated from the microbiome specimens and fecal metabolites identified. The DNA will be used to conduct DNA sequencing (metagenomics) in accordance with existing protocols through the Integrated Human Microbiome Project (iHMP) study of IBD. The fecal metabolites will be used to produce spectral profiles for quantification using protocols from the iHMP. RNA will be isolated from tissue samples and separate section preserved in Carnoy's to determine biofilm formation. RNA will be used to conduct gene expression assays to confirm taxa identified from sequencing, and blood samples will be used to conduct cytokine assay.

In compliance with BSW protocols, subjects will be screened after consent to verify eligibility. No interventions, device or drugs will be used as part of this observational study. Each participant will serve as his or her own control for the observational (and large cohort) study since this is a prospective cohort design, thus no randomization procedures will be employed. In addition, the questions being asked (e.g. whether the stool microbiome is predictive of treatment toxicity) are dependent upon the participant's baseline data.

This study will consist of potentially five study visits as described below.

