**The third through fifth study visits** (1 hour each) will take place on the 2nd(TD 15), 6th (TD 71) and 10th (TD 128) rounds of IV chemo of treatment (i.e. chemotherapy) at the BSWH center at which they are having their treatment. During this study visit, 2 blood vial samples will be taken as part of the routine clinical visit and the patient will be given two additional stool sample kits to take home to collect stool on the day before chemo starts and before chemo begins and the 2nd day and after their chemotherapy round is complete (i.e. if the infusion starts on Monday, the subject collect a stool sample on that Friday). After

each study visit, the patient will produce 2 stool samples (day before chemo starts and on the 2nd day after their chemo round ends) and drop it off at their treatment hospital or mail (FedEx) it into to the sequencing center at Baylor University. Again, they will be asked to complete the online 24 hour dietary recall (**ASA24**) at home within 72 hours of producing the stool samples. This is the same procedure that will be followed in the fourth and fifth study visits. During each of these visits, the REA or GI physician will ask about incidence and severity of chemotherapy induced diarrhea (**CTCAE – Gastrointestinal/Diarrhea, Grade 1-5**).

The REA will either call the subject or send a text message (if subject agrees) through Twillo after each visit to remind the subject of the days that stool collection and 24 hour (ASA24) recalls should occur.

The REA will obtain interval information from the participant according to the protocol and will provide subjects with stipends for each stool collection provided, which will include \$20 for each specimen collected (stool) up to \$160. If the patient was unable to provide a stool sample at the designated time point due to treatment side-effects they will still be given the compensation for completing the study. Thus, if patients complete all sample collections and all follow up visits, they may receive up to \$160.

Only [name] and the REA will have access to the data-collection sheets and registration forms that will be kept in a locked cabinet at the clinical site.

**Primary data endpoint:** At the end of the observational study we will assess incidence, duration and severity of chemotherapy-induced diarrhea.

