
#### *Medical and Symptom History:*

Specific subject information will be collected via review of the medical record(s). Specifically, data will be collected apart from that captured on the medical record, which will include minimal information on socioeconomic status (education, income), tobacco and alcohol history and medication history (**COLON-MD Questionnaire 2020-2023**). At each clinical visit after surgery and during the treatment time points, the REA will assess mucositis and diarrhea grade using the **CTCAE – Gastrointestinal/Diarrhea, Grade 1-5**.

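### Section 4.3 gives two rules for when chemotherapy-induced diarrhea is graded; under the more specific one there is no recall window, no collection of duration, and no scheduled capture from round 10 onward

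*Protocol*

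**What the plan says.** The primary endpoint in Section 4.3, Study procedures, has three components: "At the end of the observational study we will assess incidence, duration and severity of chemotherapy-induced diarrhea".

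Two places say how diarrhea is ascertained.

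- Section 4.3, Study procedures, describes the third to fifth visits, which "will take place on the 2 nd (TD 15), 6 th (TD 71) and 10 th (TD 128) rounds of IV chemo of treatment". It then says: "During each of these visits, the REA or GI physician will ask about incidence and severity of chemotherapy induced diarrhea". The scale is the CTCAE diarrhea grade. No look-back period is given and duration is not mentioned. The Visit 2 procedures in the same section list blood, stool and a dietary recall, but no diarrhea grade.
- Section 4.3, Data Collection, Medical and Symptom History, says: "At each clinical visit after surgery and during the treatment time points, the REA will assess mucositis and diarrhea grade".

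On the end of follow-up, Study procedures states: "This study will consist of potentially five study visits as described below". The fifth is on treatment day (TD) 128. Section 4.1 places the last stool on TD "131 (or the day before the next round of IV chemo) after 10 th round of IV chemo treatment", so at least one further round is expected. The calls or texts that the REA makes after each visit are reminders about stool collection and dietary recalls only.

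**The concern.** The first rule puts each inquiry at the start of a round. What the patient reports that day concerns earlier rounds, and the post-round stool is produced after the question has been asked. For round 10 no later study contact asks about diarrhea, so the TD 131 stool, one of three post-round stools per patient, has no scheduled outcome following it.

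Without a recall window, one REA may record today's grade and another the worst grade in eight weeks. Duration cannot be derived from a question about incidence and severity alone. Without a grade at Visit 2, bowel disturbance left by the resection can be counted as chemotherapy-induced.

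The Section 4.4 analyses of CID depend on this variable: the random forest and ROC classification of CID and its severity, the relation of community state types to CID, and the logistic models of CID present or absent on metabolites at baseline and at individual time points. If some affected patients are classed as unaffected, incidence is understated and associations tend to be weakened. An analysis plan cannot restore grades that were never recorded.

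**Working it through.** **1. Where the visits fall within a round.** Section 4.1 sets TD 1 as the first infusion. Round 2 on TD 15 gives a spacing of 15 − 1 = 14 days, and round 6 on TD 71 gives (71 − 1)/5 = 14 days. The first day of round r is then 1 + 14(r − 1).

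| Round | First day, computed | Visit day, stated | Post-round stool, stated | Rounds the inquiry can look back on |
|---|---|---|---|---|
| 2 | 15 | TD 15 | TD 19 | 1 |
| 6 | 71 | TD 71 | TD 75 | 2 to 5 |
| 10 | 127 | TD 128 | TD 131 | 6 to 9 |

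Two of the three stated days are reproduced exactly and the third to within one day. The example in Study procedures (infusion starts Monday, stool on Friday) is a gap of 4 days, which fits 15 to 19 and 71 to 75. For round 10, 131 − 4 = 127, so TD 128 is the first or second day of that round. Either way the inquiry comes before the post-round stool.

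**2. Gaps between inquiries.** 71 − 15 = 56 days and 128 − 71 = 57 days.

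**3. After the last inquiry.** None of the five study visits follows TD 128, while Section 4.1 expects a round after round 10. The total number of rounds is not stated. Section 4.1 also gives the length of chemotherapy as 12 weeks, or 84 days; at 14-day spacing only rounds 1 to 6 start by then, which conflicts with a round 10 visit on TD 128. Those statements must be reconciled. Here I take K = 11 or 12 rounds as an assumption.

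**4. Components of the endpoint against what is collected.** Incidence and severity are asked about at Visits 3 to 5. No named instrument asks for duration.

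**5. Illustration of size.** Section 2 refers to "chemotherapy-induced diarrhea, which affects over 50% of patients". That figure covers anti-cancer therapy for colorectal cancer in general, so I use 50% and 60% as assumed true incidence I. Assume a constant, independent risk p in each of K rounds, so that 1 − (1 − p)^K = I. With perfect recall back to the previous visit, the inquiries cover rounds 1 to 9 and the recorded incidence is 1 − (1 − I)^(9/K).

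| I | K | Recorded | Missed | Of 112 patients |
|---|---|---|---|---|
| 0.50 | 11 | 1 − 0.5^(9/11) = 0.433 | 0.067 | 7.5 |
| 0.50 | 12 | 1 − 0.5^(9/12) = 0.405 | 0.095 | 10.6 |
| 0.60 | 11 | 1 − 0.4^(9/11) = 0.527 | 0.073 | 8.1 |
| 0.60 | 12 | 1 − 0.4^(9/12) = 0.497 | 0.103 | 11.5 |

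If the same patients are affected repeatedly, the loss in incidence is smaller; it is zero if every affected patient has an episode in rounds 1 to 9 and recalls it. If only current status is recorded, the loss is larger. Even with no loss in incidence, worst grade, duration and the outcome following the round 10 stool remain incomplete.

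**The case against.** The best counter-argument is the sentence in Medical and Symptom History. It names two things, each clinical visit after surgery and the treatment time points, and Study procedures itself distinguishes a study visit from the routine clinical visit it coincides with. Read broadly, the sentence covers infusion visits in the other rounds and visits after TD 128. Section 4.3 also mentions interval history recorded at the sampling time points, interval information obtained by the REA, and review of medical records. The forms are not reproduced, and asking about incidence suggests a look-back rather than current status.

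This stands to the extent that a reader might infer that CID is assessed only on three infusion days and that diarrhea after round 10 is never captured. The document does not support that: the broad reading is open, and the other sources could pick it up.

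It does not remove the problem. None of those sources names CID, a grade or a window. The narrow reading also has support: Aim 1 speaks of three time points during FOLFOX, and Section 4.4 limits the treatment phase to three named weeks. The detailed visit procedures do not carry out the broad reading, since even Visit 2 has no grading step.

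A second tempting inference is that recorded incidence would fall to about 16 to 17%. That follows only if each inquiry captures just the preceding round (rounds 1, 5 and 9: 1 − 0.5^(3/12) = 0.159 and 1 − 0.5^(3/11) = 0.172) and if rounds are independent. The protocol does not restrict recall in that way and gives no evidence of independence.

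**Conclusion.** The concern holds as a conflict between two statements in Section 4.3, together with a gap under the more specific one. Following Study procedures, with Medical and Symptom History read narrowly, leaves CID from round 10 onward without scheduled capture and leaves earlier rounds to recall over an undefined period of up to 57 days. The absence of any instrument for duration is the firmest element, because it depends on neither reading of when diarrhea is graded.

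The size is uncertain. At 50% true incidence, about 40 to 43% would be recorded, a loss of roughly 7 to 10 percentage points or 7 to 11 of 112 patients. This rests on 11 or 12 rounds, constant independent risk and perfect recall to the previous visit, none of which the protocol establishes. It illustrates the scale and does not estimate the bias. The point still needs action before data are collected, because it concerns the primary outcome and grades missed at the time cannot be reliably rebuilt later.

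**What to change.** State one ascertainment rule and use it in both Study procedures and Medical and Symptom History:

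1. At each of Visits 3 to 5, record the worst CTCAE diarrhea grade since the previous contact, with start and end dates of each episode so that duration can be derived.
2. Ask the same question in an REA call or text after the post-round stool of rounds 2, 6 and 10, including after TD 131. The existing reminder contact can carry it if timed after the stool; otherwise one further message is needed.
3. Abstract diarrhea grade from the clinical record at infusion visits through the end of FOLFOX. Record review is already a stated data source.
4. Record the pre-FOLFOX grade at Visit 2 that Medical and Symptom History implies, list it among the Visit 2 procedures, and use it as the baseline when analysing CID.

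The cost is protocol wording and modest REA time for one extra question and the chart abstraction. No study visit is added.

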The REA will pre-screen patients that are scheduled to undergo colonoscopy to identify patients as a potential study participant. Patients scheduled to undergo colonoscopy for suspected colon cancer will be approached by the REA or Physician to ask if they would like to participate in the study and enrolled if they give consent. These informational sources will provide a short description of the study purpose and requirements for participation. Written informed consent will be obtained by the REA from patients agreeing to participate in the study and before commencement of any study activities. Once identified, the REA will screen the patients and obtain consent for study entry. After consent, participating patients will be provided with a study identification number. This number will be utilized on the data collection form, sample labeling and dietary assessments to promote confidentiality throughout the study procedures. At the consent visit, patients will complete a data collection form utilized to confirm study eligibility and record interval history at the sampling time points. Next, they will be given a stool collection kit to take home along with their bowel prep kit, to collect stool prior to bowel prep. If a positive CRC diagnosis is made through the pathology department and confirmed by GI physicians at BSWH facilities, they would continue as a participant in study. This method will allow the collection of stool specimen prior to colonoscopy. **If they are not diagnosed with stage II/III CRC, subjects will be asked if the stool sample can be used in the study as a control. Subjects will be given the option to agree or decline on the prescreening consent form.** [name] will direct the longitudinal specimen collections, assessments and retention. This consent information will be kept at BSWH by either the REA in a password protected file only accessible by the REA or [name]. We plan to recruit 112 stage II/III patients, (110% of what is needed according to power calculations). Recruitment and sample collection will be supported by the clinical practice sites in Temple and Waco, REAs, and facilitated by Principle Investigator [name] PhD, MPH, RD and Physician Drs. [name].

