#### **4.4 Data Analysis.**

Classification of taxa associated with side effects or severity: Recently, in an animal model of colon tumorigenesis (AOM/DSS), investigators used the initial microbial community structure (16s rRNA sequencing) to predict tumor burden after exposure to various antibiotics during colon carcinogenesis. In order to conduct a similar analysis and reduce data dimensionality, we will first perform cluster modeling using Dirichlet multinomial mixtures (Holmes et al. 2012) to identify microbial clusters (community state types). To determine which taxa or taxonomic cluster are the best predictors of treatment side effects (CID, mucositis) and severity (stage 3-4), we will conduct 10-fold cross-validation using the RandomForest package (Version 3.6.4) in R (R-studio, Version 0.98.1091; Boston, MA). Specifically, 5,000 trees will be used and the parameter mtry will be set at 100. The taxa with the highest importance scores will be used for further analysis. This procedure will be tested by splitting the data into test and training sets, then running Random Forest using the same procedure described above on the training dataset and comparing the predictive accuracy of the top taxa (based on importance scores) in the test set. Based on this 10-fold cross-validation, we will be able to calculate sensitivity and specificity. These top taxa will then be used to generate receiver operator curves (ROC) and calculate area under the curve (AUC). Each microbial cluster or taxa will undergo independent logistic regression testing to calculate area under the ROC curve using Stata (v13). The command roccomp will be used to compare statistical difference between AUCs and determine the best combination of taxa for classification of CID or mucositis and for severity.

Microbiome-Diet Analysis: To evaluate the impact of diet on the stool and tissue microbiome, we will use the dietary analysis generated from the ASA24 and DHQIII, which includes the Healthy Eating Index (HEI). Prior to analysis, we will conduct normality testing for each variable using Shapiro-Wilk test. For any variables that do not pass, a logarithm transformation will be performed. In order to identify any potentially important diet or nutrient-microbiome associations, we will conduct correlation analysis between dietary macronutrients (carbohydrates, fats, proteins) or micronutrients (vitamins and minerals)

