## 5. Human Subjects

### Protection of Human Subjects

#### A. Human Subjects Involvement and Characteristics

Human subjects involvement: Individuals with a positive diagnosis upon histological examination for colon cancer will be recruited from the Baylor Scott and White McClinton Cancer Center in Waco, TX and The BSWH Temple, TX locations. The Baylor Scott & White McClinton Cancer Center (BSWMCC), in Waco, Texas, and BSWH Clinic in Temple, TX provides ambulatory medical, radiation, and supportive hematology/oncology services to adults five days per week. In addition, the BSWMCC/BSWH Temple Clinics provides on-site laboratory and pharmacy services in conjunction with medical oncology and hematology care and has infusion services. The CRC Group at BSWMCC and BSWH Temple is responsible for the orchestration of day-to-day aspects of clinical research such as patient eligibility, appointments, informed consent, data collection and transcription of information from medical records onto special data collection forms.

- Patients enrolled in this study represent a vulnerable population of terminally or critically ill individuals. For this reason, those staff, Physicians and REAs, will explain with care and clarity that as a patient they will not experience any personal medical benefit from their participation in this study, but that findings may benefit future patients undergoing similar treatment. It will also be made clear that this is an observational study and will in no way impact their treatment or standard of care, and if they choose not to participate will also not affect their treatment in any way.
- Characteristics of subject population: We will recruit 112 stage II/III patients who fit our inclusion criteria (see inclusion/exclusion criteria). Baseline characteristics of current patients undergoing treatment at BSWMCC reflect the demographics of the greater Temple and Waco area: 44.7% White, 30.4% Hispanic and 21.5% Black, 1.7% Asian. During 2016, 109 total CRC cancer cases were treated (Table 1).
- 

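### Diarrhea duration is part of the primary data endpoint, but no stated question collects episode dates or a worst grade between visits 56 to 57 days apart

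*Protocol*

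**What the plan says.** All references are to the protocol.

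- **Endpoint.** Section 4.3, Study procedures, gives the primary data endpoint: "At the end of the observational study we will assess incidence, duration and severity of chemotherapy-induced diarrhea". Section 3 lists CID incidence and severity among the primary outcomes and does not mention duration.
- **Questions at Visits 3 to 5.** These visits take place on chemotherapy rounds 2, 6 and 10 (treatment days 15, 71 and 128). "During each of these visits, the REA or GI physician will ask about incidence and severity of chemotherapy induced diarrhea", using the CTCAE diarrhea scale.
- **Grading in Medical and Symptom History.** "At each clinical visit after surgery and during the treatment time points, the REA will assess mucositis and diarrhea grade", on the same scale.
- **Other routes.** The data collection form is used to "record interval history at the sampling time points". Study procedures adds: "The REA will obtain interval information from the participant according to the protocol". Medical records are reviewed, and Section 5 mentions "data collection and transcription of information from medical records onto special data collection forms". None of these is said to cover CID grade, onset or resolution.
- **Number of visits.** "This study will consist of potentially five study visits as described below". No visit at discontinuation or at the end of treatment is among those described.

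**The concern.** A primary endpoint component needs data that can produce it. Duration needs a start and a stop date for each episode. A CTCAE grade contains neither, and no later analysis plan can supply dates that were not recorded.

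The grade has a related weakness. Without a stated look-back, one site may record the grade on the day and another the worst grade since the last contact. Over gaps of about eight weeks these are different measurements. The severe cases that Section 4.4 wants to classify (its stage 3-4, read here as CTCAE grade 3-4) are sensitive to that difference.

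Secondly, if grading is confined to the study visits, an episode bad enough to end FOLFOX between rounds 2, 6 and 10 would next be asked about at a visit that does not take place. The patient's baseline stool would be in hand and the outcome label missing, for a reason tied to the outcome itself.

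**Working it through.** **1. Endpoint components against stated collection**

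| Component | Study procedures (Visits 3-5) | Medical and Symptom History |
|---|---|---|
| Incidence | asked | implied by grade |
| Severity | asked, CTCAE; reference period not stated | grade; reference period not stated |
| Duration | not named | not named |

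**2. What the visit spacing leaves open**

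Inputs: treatment days 15, 71 and 128 (Study procedures).

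- Visit 3 to Visit 4: 71 − 15 = 56 days.
- Visit 4 to Visit 5: 128 − 71 = 57 days.
- An episode wholly between Visits 3 and 4 falls within days 16 to 70, so it can last from 1 day to 70 − 16 + 1 = 55 days.
- An episode wholly between Visits 4 and 5 falls within days 72 to 127, so it can last from 1 day to 127 − 72 + 1 = 56 days.

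If only current status is asked, such an episode leaves no record. If the question looks back, it leaves a yes and a grade. In both cases the record is the same for a 1-day episode and a 55-day one.

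**3. Patients who stop FOLFOX for good, if grading occurs only at study visits**

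| Last round received | Visits 3-5 reached | Longest on-treatment stretch with no later question |
|---|---|---|
| 1 | 0 of 3 | 15 − 1 = 14 days |
| 2 to 5 | 1 of 3 | 56 days |
| 6 to 9 | 2 of 3 | 57 days |
| 10 or later | 3 of 3 | not affected between these rounds |

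The period at risk is the third column: from the last attended visit (or first infusion) to the stop.

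**4. Illustration of size**

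Only n = 112 comes from the protocol; it gives no stopping rate and no severe-CID rate. The rest is assumed: true severe CID p = 10-20%; share of these patients stopping before the next study visit q = 5-30%; share of those episodes graded nowhere else u = 0-100%.

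Severe cases missed = 112 × p × q × u.

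- Low (u = 0): 0.
- High: 112 × 0.20 × 0.30 × 1.00 = 6.7.
- Middle (15%, 15%, 50%): 112 × 0.15 × 0.15 × 0.50 = 1.26 of 112 × 0.15 = 16.8. Observed severe CID is (16.8 − 1.26)/112 = 13.9% if these patients stay in with a lower grade, or 15.54/110.74 = 14.0% if they drop out, against a true 15%.
- For scale, the binomial standard error is √(0.15 × 0.85/112) = 3.4 percentage points. The middle shift, 1.26/112 = 1.1 points, is about one third of that.

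**The case against.** The best defense concerns discontinuation. The Medical and Symptom History paragraph speaks of clinical visits, whereas Study procedures speaks of study visits. Read literally, the former can include the clinic visit at which severe diarrhea is managed and FOLFOX stopped. On that reading the gap largely closes. This stands, and it is why that half is conditional.

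A reader might infer that an early stopper loses three, two or one of three CID assessments, and so a like share of the outcome. The documents do not support that. The target is diarrhea caused by chemotherapy, and slots long after the last infusion would mostly measure something else. Missed slots are not missed cases. A reader might also take the words "This study will consist of potentially five study visits as described below" as expecting dropout. They may only reflect that patients consent before colonoscopy and continue only if cancer is confirmed.

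The defense can add that interval history, chart review and transcription exist, that asking about incidence hints at a look-back, and that the forms are not reproduced, so their fields cannot be judged absent. This is fair as to practice. But the protocol assigns none of these routes to CID dates or worst grade.

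On duration, the defense can say that no analysis in Section 4.4 uses it and Section 3 omits it, so deleting one word would also restore consistency. That is true, but it would give up a stated endpoint component and leave the look-back for severity undefined.

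**Conclusion.** The duration point holds on any reading. It is part of the primary data endpoint, and the data named for collection cannot yield it. The missing look-back for grade is of the same kind and affects severity. Both arise at collection, so an analysis plan cannot repair them afterwards.

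The discontinuation point holds only if grading is limited to the study visits and the episode is not graded through the chart or interval information. The number of patients affected cannot be determined from the protocol and may be zero. The illustrative 0 to 6.7 severe cases rests on three assumed inputs and should not be read as an estimate. A reader might infer that severe CID will be materially underestimated; the documents do not show that, and the middle example shifts the rate by well under one standard error.

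The change is worth making because it is cheap and makes a stated primary endpoint measurable.

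**What to change.** Amend Study procedures and Medical and Symptom History in Section 4.3 to agree. At each study visit, and once at permanent FOLFOX discontinuation (by phone or from the medical record), the REA records:

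- the highest CTCAE diarrhea grade since the last assessment;
- start and stop dates of each episode;
- the date of the last infusion, so that later diarrhea can be told apart from CID.

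Repeat grading at planned treatment days 71 and 128 for patients already off treatment is not needed. Section 3 should name the same endpoint components as Section 4.3.

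The cost is a short wording amendment, a few extra fields on the data collection form, and one call or chart check per early stopper. The REAs already contact patients by phone or text and records are already reviewed, so no added sample or clinic visit is required.
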